1.5.4. Calibration of the risk of malignancy

For non-imputed data, a random-effects logistic model will be used to compute both the calibration intercept and slope. The overall calibration curve will be computed using the results of the latter for an average center. The average center corresponds to a center where the calibration intercept and slope equal the fixed effect estimates (i.e. the random components are 0). Center-specific calibration curves will be computed using the empirical Bayes-estimates. For imputed data, the calibration intercept and slope will be computed per center and herein per imputed dataset by use of a logistic regression model.

Hereafter, the estimates will be combined using Rubin's Rules to get center-specific estimates and these estimates will be used in a random-effects model to get an overall estimate. For the overall calibration curve as well as for the center-specific calibration curves, this will be computed for each imputed dataset using the same method as for the non-imputed data and the results of the imputed datasets will be combined using Rubin's Rules.

The RMI does not give predicted risks. Therefore, similar to the IOTA3 validation study (Testa 2014), we will construct calibration curves conditional on the RMI score.

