For the second objective, the discriminatory ability of LR1 and the polytomous model to detect malignancy at the initial visit will be assessed. To this end, the logit of the risk of malignancy given by LR1, logit(LR1), is used to predict malignancy using logistic regression, and the performance assessed with the odds ratio, the c-index and a ROC curve. Linearity of the effect of logit(LR1) will be assessed using spline functions. This analysis is planned one year after the end of the inclusion phase of the trial. Non-operated masses will be classified as benign at the initial visit if there is an absence of a clinical diagnosis of cancer after 1 year of follow up. In addition, the ability of LR1 to predict complications during long-term follow-up will be assessed. This will be done using Cox proportional hazards regression with the logit(LR1) as predictor of complication free survival. Performance will be assessed using the hazard ratio and the c-index within the context of survival analysis. Linearity of the effect of logit(LR1) will be investigated using Schoenfeld residuals.

For the third objective, a multivariable survival analysis will be undertaken using Cox proportional hazards regression or more complex alternatives based on support vector machines (30). The models will be penalized to prevent overfitting, given that not enough events (i.e., patients that need surgery during long term follow-up) are expected for the number of available predictor variables. Internal validation will be assessed through bootstrapping rather than a split of the data in training and test sets (31).

For the fourth objective, longitudinal normative curves will be derived of the changes seen in the characteristics of non-operated masses. Longitudinal analysis techniques such as mixed models, longitudinal support vector machines, and functional linear discriminant analysis (FLDA) (32-34).

Study supervision

Central supervision: the Steering Committee is responsible for the protocol, quality control, interim analyses of the data and final analysis and reporting of the study.

Local supervision: the Principal Investigators are responsible for the data collection in their centres.

[name] is responsible for the co-ordination of the overall IOTA project and the contact between the centres.

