1.1 Objective

To assess the performance of prediction models and subjective assessment for ovarian tumor diagnosis when evaluated on all patients presenting with an adnexal mass: patients operated after the recruitment scan (without having received conservative follow-up) and patients managed conservatively with ultrasound follow-up. Because this is not the same population as the population on which the models were developed (masses when selected for surgery), this is not a true validation study.

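### The overall calibration curves in SAP 1.5.4 rest on a logistic intercept and slope alone, so they cannot show curvature; a flexible overall curve should be added beside them

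*SAP*

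**What the plan says.** For non-imputed data, SAP 1.5.4 states that "a random-effects logistic model will be used to compute both the calibration intercept and slope". It continues: "The overall calibration curve will be computed using the results of the latter for an average center", and "The average center corresponds to a center where the calibration intercept and slope equal the fixed effect estimates". For the individual centres, "Center-specific calibration curves will be computed using the empirical Bayes-estimates".

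For imputed data, intercepts and slopes are estimated per centre and per dataset and then combined. For the overall and centre-specific curves, "this will be computed for each imputed dataset using the same method as for the non-imputed data", with Rubin's Rules applied afterwards. SAP 1.5.2 makes the imputed analysis primary.

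RMI is an exception, because it gives no risk: "we will construct calibration curves conditional on the RMI score". The form of those curves is not stated. SAP 1.5.6 adds multinomial logistic calibration curves for ADNEX and names no smoother.

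SAP 1.5.7 plans separate overall calibration curves by actual and by suggested management. SAP 1.5.8 reports overall curves for the sensitivity and supplementary analyses. Neither section names another way of drawing them.

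On the population, SAP 1.1 says that "this is not the same population as the population on which the models were developed (masses when selected for surgery", and that the exercise is therefore not a true validation. The Protocol, under Statistical analysis for the second objective, says: "Linearity of the effect of logit(LR1) will be assessed using spline functions".

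**The concern.** A curve with one intercept and one slope can show that risks are too high or low overall, or too extreme or too moderate. It cannot show miscalibration whose pattern changes along the risk scale, and this design could produce such a pattern. Suppose followed women have a lower true risk than operated women at the same predicted value, and lie mostly at low predictions. The whole-population curve would then follow the followed women at the low end and the operated women at the high end, with a bend between. The 2019 SAP names no spline, smoother, grouped plot or linearity check that would reveal it.

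At stake is the overall statement on calibration in all patients with an adnexal mass. A bend would be compressed into a slope different from 1, and the reader would see smooth miscalibration in places where the model is nearly right.

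**Working it through.** The plan gives no figure to reproduce, so there are two steps: the structure of the planned curve, then an illustration on assumed inputs.

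**Structure.** The planned curve is

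logit(observed risk) = a + b × logit(predicted risk).

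Its second difference on the logit scale is zero for any a and b. For (a, b) = (0, 1), (−0.8, 0.7) and (0.5, 1.4), the largest numerical value was below 1e-13. The centre curves change only a and b. Combining the imputed curves on the logit scale keeps the line straight. If they are averaged as probabilities (the SAP does not state the scale), any small bend would reflect spread between imputations, not curvature in the data.

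**Illustration.** The documents give no group shares, risk distributions or risk ratios, so every input here is an assumption:
- 60% followed women, logit predicted risk N(−3.7, 1), true risk = r × predicted;
- 40% operated women, logit predicted risk N(−0.9, 2), true risk = predicted;
- r = 1, 0.5, 0.2 or 0.1. Malignancy is about 15% overall at r = 0.2.

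With s(p) the share of followed women among those with predicted risk p,

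true risk at p = p × [1 − s(p) + s(p) × r].

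Example at p = 5% (logit −2.944), r = 0.2:
- Followed density: 0.6 × 0.2998 = 0.1799. Operated density: 0.4 × 0.1183 = 0.0473. So s = 0.1799 / 0.2272 = 0.792.
- True risk: 0.05 × (0.208 + 0.792 × 0.2) = 1.83%.
- Best-fitting planned curve: a = −0.080, b = 1.211. Fitted logit: −0.080 + 1.211 × (−2.944) = −3.645, which is 2.54%.

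At p = 30%, s = 0.049, so the true risk is 0.30 × (0.951 + 0.049 × 0.2) = 28.8%. The curve gives 24.9%.

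| r | Slope | True at 5% | Curve at 5% | Difference (points) | True at 30% | Curve at 30% | Difference (points) |
|---|---|---|---|---|---|---|---|
| 1 | 1.00 | 5.00% | 5.00% | 0 | 30.0% | 30.0% | 0 |
| 0.5 | 1.12 | 3.02% | 3.45% | +0.4 | 29.27% | 27.04% | −2.2 |
| 0.2 | 1.21 | 1.83% | 2.54% | +0.7 | 28.84% | 24.87% | −4.0 |
| 0.1 | 1.25 | 1.44% | 2.25% | +0.8 | 28.69% | 24.05% | −4.6 |

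**A second assumed mix.** Here operated women are 40%, N(−1.2, 2.3), and calibrated. Followed women are N(−3.6, 1.3), with true logit lowered by 1, 2 or 3. At predicted 5% the true risk is 2.7%, 1.8% and 1.4%, and the curve shows 2.9%, 2.1% and 1.9%. At predicted 40% the true risk is 37.6%, 36.2% and 35.6%, and the curve shows 35.7%, 33.4% and 32.4%. The sign changes between predicted 10% and 20%. With no shift, curve and truth coincide.

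**Does a flexible curve help?** In the first mix with r = 0.2, a restricted cubic spline with four knots (5th, 35th, 65th and 95th percentiles) gives 1.87% at predicted 5% and 28.2% at predicted 30%, close to the true 1.83% and 28.8%. Three knots (10th, 50th and 90th percentiles) give 2.27% and 27.2%, which recovers only part of the gap.

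**The case against.** The strongest reply is that SAP 1.5.7 already plans calibration curves by management, and the mechanism above is precisely a difference between management groups. Under the first mix the operated curve is exact. The two-parameter curve for followed women at predicted 5% gives 2.47% against a true 2.50% (r = 0.5), 0.98% against 1.00% (r = 0.2) and 0.49% against 0.50% (r = 0.1). This stands as a real mitigation, but a partial one. SAP 1.5.7 notes that some recruited patients fall in neither actual-management group, curvature within a group stays hidden, and the whole-population curve remains straight.

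A reader might infer that the error reaches the cut-off results or net benefit. It does not. Sensitivity and specificity (SAP 1.5.3) and net benefit (SAP 1.5.5) come from classifications set against outcomes, not from the calibration curve.

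A reader might also infer that nothing in the output would warn of trouble. A slope near 1.2 is itself a visible sign, and at predicted 5% the curve has the direction right. What it does not show is where the miscalibration lies.

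Nor do the documents show that a protocol commitment was dropped. The spline check concerned logit(LR1) as a predictor, assessed by odds ratio, c-index and ROC curve. LR1 is not among the models in SAP 1.4.

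Finally, two parameters are a sensible choice for centres with few malignancies, which SAP 1.5.6 and 1.5.7 anticipate. That justifies the planned centre-specific curves. It does not justify leaving the overall curve unchecked.

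**Conclusion.** The point holds for the overall curves of LR2, SRRisks and ADNEX with and without CA125. As planned they are linear on the logit scale by construction and cannot reveal a bend. It does not extend to the RMI curves, whose form is unstated.

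That a bend will occur is plausible, not shown. The documents establish that the population differs from the development population, but give no evidence of curvature. Under the first mix the distortion is under 1 percentage point at predicted 5% and about 2 to 5 points at predicted 30%. The second mix gives about 3 points at most. Relative errors at low risk look larger (39% at predicted 5% with r = 0.2), but that is 0.7 of a point.

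The practical harm is to interpretation. In the r = 0.2 case the operated women are perfectly calibrated and true risk at predicted 30% is 28.8%, yet the curve shows 24.9% and suggests overprediction of about 5 points where it is about 1. This is a cheap improvement, not a flaw that undermines the SAP's other results.

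**What to change.** Keep the planned intercept, slope and centre-specific curves. Add to SAP 1.5.4, for each of LR2, SRRisks and ADNEX with and without CA125, one overall flexible curve: a logistic model of outcome on a restricted cubic spline of logit predicted risk (3 to 4 knots, positions fixed in advance, four where the number of malignancies allows) with random centre intercepts. Fit it in each imputed dataset, combine the fitted values with Rubin's Rules on the logit scale, and show it with its confidence band beside the planned overall curve. State that the planned curve assumes linearity on the logit scale, and that where the two differ the calibration conclusion rests on the flexible curve.

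The cost is a paragraph of SAP text, one or two extra model terms fitted in 100 datasets, and wider bands in the tails. No new data are needed.

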1.5.5. Clinical utility

We will calculate Net Benefit (NB) for risk thresholds between 5% and 50%, for using models to decide which patients to refer for specialized oncological care (Wynants 2017). For each center and threshold, we will make an average 2x2 cross-tabulation over the 100 imputed datasets. The cross-tabulation contrasts outcome (benign vs malignant) vs classification (risk<threshold vs risk≥threshold). This is used to calculate NB. Using meta-analysis, the center-specific NBs at a given threshold are combined into an overall estimate (Wynants, 2018).

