Multiple imputation will be performed to deal with missing values for CA125 and outcome. Imputations will be created using the method of fully conditional specification with the mice package in R. We will generate 100 imputations, leading to 100 completed datasets. To estimate the missing values for CA125, we will use predictive mean matching regression using the outcome, variables that are probably related to either the level of CA125 itself, or to the unavailability of CA125 (i.e. a binary indicator indicating for each patient whether CA125 was missing). As the distribution of serum CA125 was heavily skewed, the log-log transformation of CA125 will be used (i.e., $\log(\log(\text{CA125} + 1))$). In the imputation model, the following variables will be used: Presumed endometrioma, level of certainty at subjective assessment at inclusion (6 groups: certainly benign, probably benign, benign but uncertain, malignant but uncertain, probably malignant, certainly malignant), patient age, type of center (oncological versus non-oncological center), lesion largest diameter, proportion of solid tissue (maximum diameter solid component divided by maximum diameter of lesion), number of locules (1, 2-10, >10, other), number of papillations, presence of shadows, presence of ascites, presence of metastases, bilaterality, pelvic pain, personal history of ovarian cancer, papillary height, papillary flow, color score, echogenicity of cyst fluid, and outcome (benign, borderline, stage I primary invasive, stage II-IV primary invasive, secondary metastatic). Descriptive characteristics of the tumor were based on the inclusion scan. Uncertain outcomes (cf above) will be considered missing, and hence the outcome will be imputed).

Note that some patients are classified as having a malignant tumor based on clinical and ultrasound information during follow-up (cf category M3 above). For these patients, we do not have a classification into one of the malignancy subtypes. The multiple imputation procedure will therefore treat the outcome as missing such that it will be imputed. The imputed outcomes will be evaluated, and the most commonly imputed malignant type will be used as the outcome in the analysis.

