1.5.3 Discrimination between benign and malignant tumors

We will calculate the c-statistic (i.e. AUC) per center, and calculate an overall AUC using random effects meta-analysis on the logit of the center-specific AUCs. In case multiple imputed data are used (e.g. models that include CA125, or when multiply imputed outcome are used), the $\text{logit}(AUC)$ is calculated for each center and herein for each imputed dataset. The latter estimates will then be combined using Rubin's rules and the resulting estimates will be used in a random-effects model to get a final estimate of the AUC.

Sensitivity and specificity will be calculated at the following cut-offs (for models that give predicted risks): 1%, 3%, 5%, 10%, 15%, 20%, 25%, 30%, 40%, and 50%. For the non-imputed data, a bivariate random-effects model will be used to calculate an overall result that takes the clustering by center into account. For imputed data, center-specific sensitivity and specificity as well as their variance (i.e. standard error squared) will be computed, and combined using Rubin's Rules to obtain a final center-specific estimate. These will be used in a bivariate random-effects model to come to a final estimate.

For RMI, we will use cut-offs of 25, 100, 200, and 250. For the Simple Rules classification, we will combine the inconclusive cases with the cases classified as malignant, i.e. inconclusive cases will be classified as malignant.

Because risk models and RMI are on a different scale, it is difficult to directly compare sensitivity or specificity. Therefore, we also calculate the sensitivity when fixing the specificity at 90%, and the specificity when fixing the sensitivity at 90%.

For subjective assessment, we will quantify the overall sensitivity and specificity using a bivariate random-effects model.

For Simple Rules, we will report the percentage of inconclusive cases, and specificity and sensitivity when inconclusives are classified as malignant. This will be done using meta-analysis techniques.

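### SAP 1.5.5 averages the 2x2 tables over imputations before pooling net benefit, so between-imputation variance is left out of the centre variances, the pooling weights and any interval

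*SAP*

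**What the plan says.** In the SAP of 28 May 2019, section 1.5.5 opens: "We will calculate Net Benefit (NB) for risk thresholds between 5% and 50" per cent, "for using models to decide which patients to refer for specialized oncological care". For each centre and threshold, "we will make an average 2x2 cross-tabulation over the 100 imputed datasets". The classification rule is: "The cross-tabulation contrasts outcome (benign vs malignant) vs classification (risk<threshold vs risk≥threshold"). Then: "Using meta-analysis, the center-specific NBs at a given threshold are combined into an overall estimate". The section gives no variance formula, no interval and no step for combining imputations other than the averaging. It cites a methods paper on random-effects meta-analysis of clinical utility.

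Section 1.5.1 explains where the imputations come from: "We will generate 100 imputations, leading to 100 completed datasets". Section 1.5.2 makes imputed CA125 and imputed outcome the basis of the primary analysis. It names RMI and ADNEX with CA125 as the models that need imputed CA125.

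Sections 1.5.3 and 1.5.4 treat imputed data differently. Centre-specific logit AUC, sensitivity and specificity, and calibration intercept and slope are obtained per imputed dataset and combined by Rubin's Rules before the random-effects step. For sensitivity and specificity the variances are mentioned explicitly.

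On tools without a risk, 1.5.4 says "The RMI does not give predicted risks" and 1.5.3 says "For RMI, we will use cut-offs of 25, 100, 200, and 250". Section 1.5.3 also counts inconclusive Simple Rules results as malignant, and 1.4 treats subjective assessment as a binary judgment.

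**The concern.** Multiple imputation yields two components of uncertainty: the sampling variance within a completed dataset and the variance of the estimate across completed datasets. Averaging the 100 tables keeps the mean of the estimates and discards their spread. If the averaged table is then handled like a table of observed women, the second component is missing.

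Three quantities depend on that variance: the centre standard error, the weight each centre receives, and any interval around the pooled net benefit. The weights matter because the share imputed may differ between centres. Section 1.5.1 expects CA125 to be measured more consistently in some centres than in others, and the follow-up SAP (1.1) describes marked differences in adherence to follow-up. A centre with much imputed data would look more precise than it is. Selecting centres with good data limits this but need not remove it.

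The planned sensitivity analyses would not reveal the problem. Section 1.5.8 reports only c-statistics and calibration curves, so no net benefit is planned with the uncertain outcomes excluded.

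**Working it through.** The plan states no net-benefit value, variance or share of missing data, so there is no figure to reproduce. The steps below use the standard definition, with assumed inputs marked as such.

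**1. Point estimate.** With w = t/(1−t), NB = TP/n − w × FP/n. A centre's n is the same in every imputation, so the mean of the 100 values is mean(TP)/n − w × mean(FP)/n. That is exactly the NB of the averaged table. In simulation the largest difference was about 2 × 10⁻¹⁶, which is rounding error.

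**2. Variance.** With A = TP/n and F = FP/n, the sampling variance in one table is V = [A + F w² − (A − F w)²]/n. Let W be the mean of V over imputations and B the variance of NB between imputations. Rubin's total is T = W + (1 + 1/100)B. Putting the averaged table into V gives about W + B/n, because only the squared term is non-linear. At n = 100 it keeps about 1% of B.

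**3. One case by hand.** Assumed: n = 100, prevalence 20%, sensitivity 0.90, specificity 0.85, 20% of outcomes imputed at random within classification, t = 10%.

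- A = 0.18, F = 0.12, w = 1/9, NB = 0.18 − 0.0133 = 0.1667.
- W ≈ (0.18 + 0.12/81 − 0.0278)/100 = 0.001537, so SE = 0.0392.
- Of 30 test-positive women, 24 have an observed outcome (14.4 malignant, 9.6 benign) and 6 are imputed. With a Beta(0.5, 0.5) prior the malignant proportion is drawn from Beta(14.9, 10.1), mean 0.596. The imputed malignant count has variance 6 × 0.596 × 0.404 × 31/26 = 1.72.
- Moving one woman from FP to TP changes NB by (1 + w)/n = 0.01111, so B = 1.72 × 0.01111² = 0.000213.
- T = 0.001537 + 1.01 × 0.000213 = 0.001752, so SE = 0.0419.
- Ratio 0.0419/0.0392 ≈ 1.07. The simulation gave 1.068 for this setting.

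**4. Range.** One-centre simulation with 2,000 repetitions per setting. Assumed: n = 100 or 300, prevalence 10, 20 or 30%, t = 5, 10 or 50%, same sensitivity and specificity.

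| Outcomes imputed | Rubin SE / averaged-table SE | SE understated by | Coverage of nominal 95% interval, averaged table | Coverage, Rubin |
|---|---|---|---|---|
| 10% | 1.023–1.052 | 2–5% | 91.8–94.5% | 93.0–95.3% |
| 20% | 1.051–1.114 | 5–10% | 90.7–94.3% | 93.1–95.3% |
| 30% | 1.085–1.187 | 8–16% | 88.2–93.0% | 92.5–95.5% |

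The understatement is 1 − 1/ratio; for example, 1 − 1/1.187 = 16%.

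A separate simulation with N = 3,000, t = 10%, CA125 missing in 20–60% and outcome in 5–15% (all assumed) gave SE ratios, without to with B, of 0.946 to 0.983. That is 2–5% too small.

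**5. Weights.** Take two centres of n = 100 at 20% prevalence and t = 10%, one with 10% and one with 30% of outcomes imputed. The SE ratios are 1.031 and 1.111. With no between-centre variance, inverse-variance weights are inflated by 1.031² = 1.064 and 1.111² = 1.235. The more heavily imputed centre gains 1.235/1.064 = 1.16, or 16%, relative to the other. Any between-centre variance shrinks this.

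**6. Secondary point: RMI cut-off.** Assumed sensitivity/specificity pairs 0.93/0.55 and 0.62/0.94, prevalence 20%.

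- At t = 5%, NB is 0.186 − 0.36 × 0.0526 = 0.167 for the first pair and 0.124 − 0.048 × 0.0526 = 0.121 for the second.
- At t = 50% it is 0.186 − 0.36 = −0.174 and 0.124 − 0.048 = 0.076.

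The ranking reverses, so if RMI is included the cut-off should be fixed in advance.

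**The case against.** The best defence is that 1.5.5 promises no interval and states no variance formula. It speaks only of an overall estimate and cites a methods paper that may handle variance in some other way. That is fair: this is an unspecified step, and no stated figure is wrong. But a meta-analysis needs a variance or a model for each centre's counts. The only input described is the averaged table, from which the between-imputation spread cannot be recovered.

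A second defence is that the effect is small. At low missingness it is. In a random-effects model the between-centre variance may also absorb part of what is lost within centres, so the pooled interval can be affected less than the centre standard errors. Both points stand and limit the importance of the matter.

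A reader might go further and infer that net benefit cannot be obtained for RMI, Simple Rules or subjective assessment, or that an RMI score would be compared with 0.05 to 0.50. The documents do not support this. Net benefit needs only a 2x2 table and a threshold. Section 1.5.3 supplies RMI cut-offs and a rule for inconclusive Simple Rules results, and 1.4 makes subjective assessment binary. Section 1.5.3 also says that RMI is on a different scale and reserves percentage cut-offs for models that give risks. The wording on risk thresholds in 1.5.5 therefore most naturally limits it to those models. That would be a legitimate choice, and subjective assessment is in any case outside the model list. Only a clarification remains.

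**Conclusion.** The point holds in a limited form. As written, 1.5.5 leaves out between-imputation variance, whereas 1.5.3 and 1.5.4 include it. Imputed outcomes affect every tool; imputed CA125 adds to this for ADNEX with CA125, and for RMI if it is included. Centre variances would be too small, the weights would carry that error, and any interval would tend to be too narrow.

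The size is a 2 to 16% understatement of the centre standard error for 10 to 30% of outcomes imputed, and 2 to 5% under the other set of assumptions. All of this rests on assumed missingness, prevalence, accuracy and centre size, and on the averaged table being treated as observed data. The pooled effect was not quantified.

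It would be wrong to conclude that the centre net benefits are biased by the averaging, because they are identical to the Rubin estimates. The pooled estimate could move only through the weights. This is a worthwhile refinement, not a threat to the study's main results.

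**What to change.** In 1.5.5, replace the averaged table by this sequence: for each centre, threshold and imputed dataset, compute net benefit and its variance; combine the 100 pairs by Rubin's Rules into one centre estimate and variance; then meta-analyse across centres. Running the meta-analysis within each imputed dataset and pooling the results is an acceptable alternative. State whether an interval will be reported. The cost is a few sentences, modest computing and slightly wider intervals; centre point estimates do not change.

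As a secondary clarification, state which tools 1.5.5 covers. If tools without a predicted risk are included, say that RMI at each 1.5.3 cut-off, Simple Rules with inconclusive counted as malignant, and subjective assessment enter as fixed classifications at every threshold. If they are not included, one sentence saying so is enough.
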